#### b. Sources of research materials

All information pertaining to this project (e.g., screening forms, questionnaire data, interviews, digital recordings of assessment and treatment sessions) will be held in the strictest confidence, will be kept in a locked file (digital recordings will be held in a pass-word protected computer server), and will be available only to individuals directly involved with the project. Under no circumstances will individually identifiable data be released to anyone without written consent of the participant. Results will be published as group findings only. Assessment and treatment results will be discussed with the participant only.

### **Potential Risks**

Treatment: Some risks are associated with the administration of any psychosocial treatment. In this study, the primary risk for both GCBT and SGP is the evocation of uncomfortable levels of anxiety or other emotions during the treatment sessions. Some patients may find sessions or assignments stressful and react to them with anxiety or anger. The GCBT carries an additional risk that exposure-based homework assignments may carry a likelihood of temporarily increasing PTSD symptoms. Recognizing this, the therapists assigned to this condition will alert participants to expect a possible increase in symptoms, to facilitate management of this should it occur. In addition, there will be a period of time between when participants are initially assessed and when there are a sufficient number of participants to randomize to a group treatment. We do not anticipate any adverse effects while participants are waiting for the group to begin. However, these individuals will be regularly monitored by the project coordinator and by Drs. [name] and [name] at their respective sites.

Recording: Some participants may feel uncomfortable about the assessment and treatment sessions being recorded (necessary for supervision and treatment adherence checks). However, this will be a required procedure. The purpose of the recording will be explained, confidentiality will be respected, and both informed consent and authorization for recording will be obtained as per requirements put forth by the Healthcare Information Portability and Accountability Act (HIPAA). Digital recordings will be marked only by subject identification codes, stored on a secured server that is pass-word protected, and only available to study personnel. Adherence rating sheets will also be stored in a locked cabinet located within the project coordinator's office.

Diagnostic Interviews, Self-Report Measures and Assessor Ratings: Some discomfort associated with the recording may occur as well as some potential distress when discussing traumatic experiences during the assessment interviews. These situations will be handled as described above.

## **E. 2. Adequacy of protection against risks**

### Recruitment and Consent Procedures

Veterans will be recruited through the various clinics at the VA Boston and VA Providence sites. Given that we are recruiting at two sites that are relatively large and have demonstrated past successful recruitment for multiple PTSD clinical trials, we anticipate no problems recruiting the targeted sample size.

In accordance with HIPAA regulations, written informed consent will be obtained from each participant after a thorough explanation of procedures by a project staff person and the opportunity for the participant to ask and receive answers to questions. Participants will be informed of the nature of the investigation, the types of assessments and treatment involved, the potential risks involved in participation and will be asked to sign an informed consent statement prior to participating in the proposed study. In addition, the participant will receive an explanation of how their information will be handled including all parties involved, data management, and plans to publish data in group format without identifying information.

Participants will also be informed that if suicidal or homicidal intentions are disclosed, confidentiality may be broken in order for protective measures to be taken. Although there will be no questions asked in the assessments regarding children or geriatric persons, if a participant were to disclose child or elder abuse, appropriate agencies would be contacted and participants will be so informed in the consent form. See the Data Safety and Monitoring Plan (Section E.5 below) for specific information on assessment of suicidal information and at what point action(s) would be taken.

### Protection against risk

We will carefully screen to identify individuals whose risk for potential adverse outcomes is elevated were they to participate in the proposed research. Such individuals will be excluded from the study. As an example, an actively suicidal person would be excluded from study participation and appropriate clinical care and referrals will be provided. The exact nature of "appropriate clinical care" will be determined by the judgment of clinicians and supervisors familiar with the specific participant and that person's access to community resources, and may include cognitive-behavioral treatment, other psychotherapy, referral to inpatient treatment or referral for medication treatment.

Clinical staff are trained to cope with any anxiety/distress experienced by participants during the assessments and treatment.

All personnel proposed for this project will have the required ethics, human subjects, and confidentiality training, which include information about maintaining data integrity and security.

Careful monitoring of participants during the pretreatment period and all phases of study participation will be conducted by the project staff. Each participant will see the same clinicians for each of their treatment visits. While waiting for a group to begin and during the follow-up interval, each participant will receive regular check-ins from the project coordinator. The project coordinator will be a Ph.D. level therapist who is trained to provide supportive services, as well as recognize if a participant is so distressed as to warrant exclusion from the trial. In particular, during the interval preceding the start of treatment as well as during the follow-up interval, the project coordinator will contact each participant once every 3-4 weeks, in order to determine how he is feeling and functioning (see below for further discussion of this choice). Veterans will be told to contact the project coordinator in case of emergencies or the respective VA after hours call line, which provides psychiatry on call service.

Explicit criterion for exclusion during the course of the trial are as follows:

1. Reporting of psychotic symptoms
2. Actively suicidal or homicidal (with intent)
3. Displaying repeated disruptive behavior within the group treatment setting (examples include being sarcastic towards therapists or other group members, routinely arriving late by 30 minutes or more, hi-jacking the scheduled group content in order to direct attention to his own agenda). If there is a question about an individual's behavior during group, [name] will review the treatment recording and determine, in consultation with the other investigators on this application, if the veteran should be dropped from the trial.

Participants will be instructed to contact study personnel at any time (including during the follow-up interval) in the event of worsening of symptoms or relapse. Participants whose clinical condition has deteriorated will be removed from the study and given appropriate clinical care.

Participants failing to benefit from the study treatments will be provided with, or referred to, appropriate clinical care. Participants who begin treatment and experience adverse outcomes sufficient to require removal from the study will receive appropriate clinical care.

As in any type of treatment or clinical research program, participants' confidentiality must be carefully guarded and respected. All data with identifying information will be stored in locked files or password-protected computer files. Data being analyzed will be identified by subject codes, and identifying information will be removed. The identity of participants will not be revealed in the presentation or publication of any results from the project. All project staff will be educated about the importance of strictly respecting participants' rights to confidentiality and will have completed relevant training courses including proper practice in accordance with HIPAA regulations, protection of human subjects, and computer security.

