The study analyses will include all cases that were randomized into the trial, including individuals who dropped out of treatment. Thus, the distinction between ITT and completer analyses becomes artificial. Greater detail about the proposed analytic approach is discussed in the next section. We intend to contact participants who voluntarily drop out of treatment during what would have been their mid, post- and follow-up assessments, in order to provide as complete a data set (and effect size estimates) as possible.

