
***Hypothesis 2.*** Reductions in PTSD symptom severity will be maintained in the GCBT group at 12-month follow-up. Much as with Hypothesis 1, multilevel latent growth modeling will be used. In the analyses to examine Hypothesis 2, we will not include the treatment condition covariate but will include the site dummy code, to examine potential site differences. To test the prediction that the means of 6mos and 12mos do not differ, the slope factor loadings corresponding to these two time points will be constrained to equality and compared to the fit of a latent growth model where the 6 mo time point was freely estimated ( e.g., Baseline model:  $0^{* * 1}$ ; hypothesized model:  $0^{* * 1} 1$ ).

The **secondary aim** is to examine the generalizing effects of both GCBT and *SGP* on co-morbid conditions, distress and impairment. Because most trials in the PTSD literature do not include a thorough assessment of treatment generalization, it is unknown whether available treatments only address PTSD or whether gains generalize to related domains of functioning, including co-

morbid conditions such as depression, generalized anxiety, and alcohol use. Three hypotheses are proposed:

**Hypothesis 3.** For patients who are diagnosed with co-morbid Major Depressive Disorder (MDD), Generalized Anxiety Disorder (GAD), and/or Alcohol abuse prior to treatment, GCBT will produce significantly larger symptom reductions for these conditions, relative to SGP at post-treatment assessment and these generalized changes will show stability at 6 mo follow-up (FU). To test this hypothesis, we will use multi-level analysis, as discussed for Hypothesis 1. For continuous variables (BAI, BDI-II, SIP), we will use the same approach as described for Hypothesis 1. Although latent growth modeling can accommodate categorical outcomes (e.g., MDD+, MDD-) with an appropriate estimator (e.g., robust weighted least squares, maximum likelihood with numerical integration), there is concern about the estimation failure resulting from low cell frequencies, particularly at post-treatment and follow-up. In the event that cell frequencies are too low, we will augment the analyses from the continuous variables with more descriptively oriented statistics showing the rates of comorbidity decline at each assessment point as a function of treatment condition.

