**E. 5. Data Safety and Monitoring Plan (DSMP)**

The VA's Centralized Data Monitoring Committee (DMC) will monitor this study. The DMC focuses on participant safety and accrual as well as on statistical issues. In general, the DMC will serve as an oversight committee, reviewing any modifications to the research design and conduct of the study and making recommendations.

Regarding the safety of participants, the DMC will review new risk management protocols and modifications to risk management protocols. The DMC will also review procedures and decisions regarding the adequate protection of specific participants when investigators move into risk management protocols because of adverse events or clinical deterioration. When appropriate, the DMC will serve as final arbiters of whether individual participants should be removed from the protocol.

The DMC will be in contact at least once per year with the PI and Co-I's in order to review progress reports and discuss issues relevant to study safety. Following each meeting, a summary of the board's review will be provided to the research team. They will also be available to review emerging data (in the study or the literature) which may alter the risk/benefit ratio and will be empowered to decide upon continuation, discontinuation, or termination of the study. In addition, study enrollment data will be submitted to the DMC on a quarterly basis in order for the DMC to monitor recruitment success on the project.

Data Monitoring Plan. Data will be collected using standardized forms and will only be identified using the participants ID number (no names or identifying information will be on the forms). The codes that link the names of participants and their ID numbers will be kept confidential by the site PI's in a secured, locked cabinet located within their office. These data will only be accessible to the site PI's and staff directly working with the study. All data will be entered on-line, with 100% review by the project coordinator in those instances where a

discrepancy occurs during double entry. Data will be double-entered by trained staff member, and data entry discrepancies will be corrected by the Project Coordinator, based on source documents. The quality of the data will be monitored on an ongoing basis.

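### Men whom the investigators remove for deterioration have no planned outcome assessment, which tends to understate loss of GCBT gains in Hypotheses 2 and 5

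*Combined protocol and SAP*

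**What the plan says.** Section E.2, Protection against risk, sets the removal rule: "Participants whose clinical condition has deteriorated will be removed from the study and given appropriate clinical care". It speaks of the study, not of treatment, and gives neither a threshold nor a time window. The sentence before it reads "Participants will be instructed to contact study personnel at any time (including during the follow-up interval) in the event of worsening of symptoms or relapse". The same section states that "during the follow-up interval, the project coordinator will contact each participant once every 3-4 weeks", and that the coordinator is trained to "recognize if a participant is so distressed as to warrant exclusion from the trial". It also lists psychosis, active suicidal or homicidal intent, and repeated disruption of the group as grounds for exclusion during the trial. In section E.5, where appropriate, "the DMC will serve as final arbiters of whether individual participants should be removed from the protocol".

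On outcome data, the Analytic approach text just before D.7.a keeps every randomised man in the analysis and says "We intend to contact participants who voluntarily drop out of treatment during what would have been their mid, post- and follow-up assessments". Missing values are handled by direct maximum likelihood, which assumes they are missing at random. Sensitivity analyses under not-missing-at-random assumptions are promised, without scenarios.

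Hypothesis 2 (D.7.a) concerns the GCBT arm alone. It constrains the 6- and 12-month slope loadings to be equal "To test the prediction that the means of 6mos and 12mos do not differ". Hypothesis 5 uses the same approach for distress and impairment, measured by SF-36 subscales.

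**The concern.** The re-contact rule misses two kinds of removed men. A man taken out by the investigators has not left voluntarily. A man taken out during follow-up has not left treatment at all, because treatment is over; all that removal can end is his assessments. Read together, the two rules leave both kinds without a planned CAPS-5 or SF-36. That sits badly with the plan's stated wish for the fullest possible data on everyone randomised.

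The loss is also informative. The trigger is clinical worsening, often picked up in a call or check-in between scheduled assessments, so the score that would have shown the worsening is never taken. Because a finding of no difference supports Hypotheses 2 and 5, losing the men who got worse pushes the result towards the trial's own prediction. Durability to 12 months is part of the primary aim.

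**Working it through.** The plan states no relapse or removal rate, so it has no figure on this point to reproduce. The steps below show direction and scale under stated assumptions.

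**1. Is there an assessment route elsewhere?** The nearest text is the section E.5 rule on discontinuation after a serious adverse event. The site PI then monitors the man's status until the event resolves, is judged unrelated, or ends in death. That is safety follow-up, not the outcome battery. No other text schedules outcomes for a removed man.

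**2. When does maximum likelihood fail?** One simulation of 1,000,000 men used 6- and 12-month scores in SD units with an assumed correlation of 0.5 or 0.7.
- Removal depending only on the recorded 6-month score: bias of 0.002 SD or less.
- Removal following worsening after month 6: loss understated in every scenario, by about 0.05–0.08 SD (5% removed), 0.09–0.16 SD (10%) and 0.13–0.23 SD (15%).

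For scale, the standard error of the 6-to-12-month change with 98 men is 0.08–0.10 SD, or 0.10–0.13 SD if the design effect 1 + (7 − 1) × 0.11 = 1.66 is applied.

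**3. Size of the understatement.** Let π be the share of GCBT men who relapse between months 6 and 12, D the shift in SD, and f the share of relapsers removed before the 12-month assessment. If relapse is unrelated to earlier scores:

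- true loss = πD
- estimated loss = πD(1 − f)/(1 − πf)

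Example: π = 0.20, D = 1.0, f = 0.5 gives 0.20 × 0.5/(1 − 0.10) = 0.10/0.90 = 0.11.

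A simulation of 200,000 men agrees. It used six visits, random-intercept variance 0.6, residual variance 0.4, a gain of 1.0 SD, and maximum likelihood with an unstructured normal model:

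| Relapse, shift | f = 0 | 25% | 50% | 75% | 100% |
|---|---|---|---|---|---|
| 20%, 1.0 SD | 0.20 | 0.16 | 0.11 | 0.06 | 0.00 |
| 10%, 1.0 SD | 0.10 | 0.08 | 0.05 | 0.03 | 0.00 |
| 20%, 0.5 SD | 0.10 | 0.08 | 0.06 | 0.03 | 0.00 |

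If relapse also depends on the 6-month score (logit slope 1.0 per SD), the 20%, 1.0 SD case gives 0.12 with half removed and 0.00 with all removed.

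**4. Chance of detecting the loss.** A paired t-test on 98 men, ignoring clustering, stands in for the plan's model-fit comparison. Hand check for 20% and 1.0 SD:
- None removed: variance of the difference = 2 × 0.4 + 0.20 × 0.80 = 0.96; SE = √(0.96/98) = 0.099; 0.20/0.099 = 2.02; Φ(2.02 − 1.96) = 0.52.
- Half removed: 98 × 0.90 = 88 men; variance = 0.80 + 0.111 × 0.889 = 0.899; SE = √(0.899/88) = 0.101; 0.111/0.101 = 1.10; Φ(1.10 − 1.96) = 0.19.
- All removed: no loss remains in the data, so 5%.

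In 4,000 simulated trials, detection for none/half/all removed was 52/19/5% (20%, 1.0 SD), 17/9/5% (10%, 1.0 SD) and 18/9/5% (20%, 0.5 SD).

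**5. Between arms.** With a 1.0 SD shift and all relapsers removed, equal relapse in both arms gives a bias in the 12-month difference of about 0. With 10% against 20% the bias is 0.10 SD: against GCBT if fewer GCBT men relapse, in its favour if more do. The direction for Hypothesis 1 is therefore unknown.

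**The case against.** No sentence forbids assessing a removed man; the gap is inferred from the removal rule and from silence elsewhere. Deterioration is not on the explicit exclusion list, and other text tolerates distress: section D.3 (Care Path) expects residual problems to be found at follow-up and referred, and E.5 allows increased suicidal ideation to be managed within the protocol. On a narrow reading, removals could be few. This stands as a limit on size. It does not supply an assessment for the men who are removed.

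The calculated bias belongs to one window: relapse after the 6-month assessment and removal before the 12-month one. Men removed during treatment, including all those removed for disrupting a group, lack both scores, and the effect on the 6-versus-12-month contrast is then uncertain. Worsening already captured in a recorded score is largely corrected. Both points stand.

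The headline case needs 20% of men to relapse by a full SD, with half or all of them removed. With a quarter removed the bias is 0.20 − 0.16 = 0.04 SD. Even with nobody removed, detection is only 52%, so part of the weakness of Hypothesis 2 lies in treating no detected difference as support, which is a separate matter.

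The planned not-missing-at-random analyses, the weekly PCL-5 during treatment and the DMC's role soften the problem. None of them supplies a follow-up outcome that was not collected.

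Finally, removed men will receive other care, possibly including CBT, and may improve because of it. Their later scores would include that benefit, so continued assessment does not recover the loss that would have occurred without rescue care. It does give the 12-month mean for all randomised men, the set the plan says it will analyse.

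**Conclusion.** The concern holds and should be fixed. As written, the plan makes loss of outcome data depend on deterioration and limits re-contact so that investigator-removed men are not covered. For worsening after month 6 that goes unrecorded before removal, the bias is towards no change, which favours Hypotheses 2 (CAPS-5) and 5 (SF-36). The size cannot be known from the documents. Under the assumed 10–20% relapse by 1.0 SD, half the relapsers removed roughly halves the estimated loss, and all removed hides it. At 10% relapse the gain from fixing this is mainly a correct estimate, since the test would seldom change. An effect on the between-arm contrast is possible but of unknown direction. Confidence is high on the gap in the rules and on the direction in that window, not on the magnitude.

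**What to change.** Keep every clinical stopping rule. In section E.2, state that removal ends study treatment only. Unless he withdraws consent or assessment would be clinically unsafe, a removed man is still invited to each scheduled blinded CAPS-5 and to the self-report battery, including the SF-36. In the Analytic approach text, delete the word *voluntarily* and make clear that re-contact also covers men removed during follow-up. Record the date and reason for each removal and report removals by arm. An extra CAPS-5 at the time of removal is optional.

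The cost is protocol and consent wording plus a little tracking effort. The assessments are already scheduled for all 196 men. Some removed men will decline. Others will be receiving other care, and the report should say that their scores reflect it.

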**E. 3. Potential Benefits of the Proposed Research to the Subjects and to Others.**

a. Potential Benefits

The direct benefit to participants who enter this study will be to obtain relief from PTSD symptoms, decreased avoidance, decreased disability, and increased quality of life. For many participants, PTSD has greatly impeded their social, vocational, and family functioning.

**E. 4. Importance of the Knowledge to be gained**

PTSD is a chronic and debilitating disorder and is particularly prevalent in the veteran population. Although we now have a number of first line treatments available, all of these first-line treatments are delivered in an individual format. This is unfortunate as there is a great need for group treatments. As is true for many medical centers, the VA Healthcare System does not have sufficient providers to provide individual services to all of the veterans who present for PTSD treatment. Thus, it is imperative that we identify efficacious group-based treatments for PTSD in order to be able to adequately serve those in need of PTSD treatment. The primary aim of the study proposed here is to examine the efficacy of a group-based cognitive-behavioral treatment for PTSD that has been shown to be efficacious in a sample of participants with PTSD resulting from a motor vehicle accident.

